9.2. Setting

This study aims to look at de novo AML patients who have received GO as 1L therapy in Austria, Belgium and Germany. Some Austrian and all Belgian and German patients' data will be captured via chart review; the data sources and the method of data collection for the Austrian secondary dataset is outlined in [Section 9.4](#). Potential sites participating in the retrospective chart review were invited to complete a short feasibility questionnaire prior to site selection. The feasibility questionnaire was used to confirm suitability of sites for inclusion, confirming study critical information such as GO patient caseload and data availability. Additionally, logistical information pertaining to site contracting and IRB processes will also be assessed. Following this, eCRFs will be completed by clinicians and site staff at the site for patients meeting the inclusion/exclusion criteria below.

Patients aged 18 years and above with a diagnosis of de novo AML between 01 April 2018 and 31 May 2023 (indexing period) will be identified within the sites/datasets using the inclusion and exclusion criteria specified below. The indexing period should allow for a large proportion of patients treated with GO in these countries/sites to be gathered, following EMA approval in April 2018. No formal sampling will be conducted in any country. Sites selected for a chart review methodology will complete data collection for all eligible patients and all data collected on eligible patients captured in secondary datasets will be extracted.

[figure not shown]
There are minimal inclusion/exclusion criteria ([Section 9.2.1](#) and [9.2.2](#)) in order to maximize the number of GO-treated patients eligible for this study. Inclusion criteria were designed to reflect the population GO is indicated for and to align with the phase III ALFA-0701 clinical trial¹ (inclusion criteria 1 – 4, exclusion criteria 1 - 2). Patients must have data available for a minimum of 3 months after initiation of GO-regimen to capture data relating to effectiveness outcomes (eg, time to next treatment, survival; inclusion criteria 5). If required by country IRB, patients (or a legally acceptable representative) will need to provide a personally signed and dated informed consent form for their data to be extracted from their medical records (inclusion criteria 6).

Each data source is likely to capture a large proportion of GO-treated patients in that country, hence their selection. The Austrian, Belgian and German centres have been selected as they meet the feasibility requirements (capture the relevant data variables) and due to the sample size of GO patients that they contain. The Austrian Myeloid Registry recruits data on patients with myeloid diseases from 15 Austrian centres (excluding the Medical University of Vienna) with an estimated enrollment of 3000 patients. The eligibility criteria below are largely based upon the recommend use of GO; ensuring that the overall patient sample gathered will be clinically representative of the GO treated population.

The initiation date of 1L treatment within the indexing period will be defined as the index date. De novo AML diagnosis will be captured within the screening questions of the eCRF and fully defined for each data source within the Statistical Analysis Plan (SAP). Baseline patient demographics and clinical characteristics will be evaluated at index. Treatment patterns and effectiveness outcomes will be described throughout the follow-up period. Patients will have a minimum follow-up of 3 months defined as patients with 3 months of data, following the 1L treatment initiation. This will allow for assessment of treatment patterns and early effectiveness outcomes. Follow-up will end with the following endpoints: death, loss of data (eg, transfer to a new hospital) or end of the study period. In order to maximise the follow-up data captured necessary to accurately assess survival outcomes (EFS, RFS and OS), follow-up will extend up until either the last data available for the patient (in Austrian, Belgium, and German sites), or the date of database extraction (in the Austrian Myeloid Registry). Patients who have limited follow-up data which is not sufficient for the assessment of OS and accurate EFS and RFS, will be right-censored for the purpose of survival outcome specific analysis. Patients who die within the 3-month follow-up period would be considered eligible for inclusion in order to evaluate EFS, RFS and OS outcomes.

Figure 1. Study Schematic

Study Schematic–eCRF and secondary data dataset design

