- Missing data from the eCRF is an important limitation to consider in this study. Some variables that we intend to collect may not be present within a patient's medical record and so cannot be extracted during the eCRF. To address this limitation, the standardised eCRF will undergo a thorough review process prior to implementation which will help ensure that the content is appropriate for the listed research objectives and can reasonably be expected to be captured within patients' medical notes. Further, the eCRF will be designed in such a way that incomplete variables will be flagged and eCRFs will not be able to be locked until all variables have been completed. Where data is not available in Austria and Belgium, the sites will be asked to provide an explanation for the missing data, thus providing the opportunity to capture data not provided during initial data entry. In Germany, it is important to note the additional limitation that data will need to be completely anonymised, meaning a patient linkage file cannot be created and thus, it will not be possible to query patient data that requires identification through a linkage document.
- Secondary data often poses a limitation in regard to data lag. The Austrian Myeloid Registry may not have data for patients available to the present day – the data lag associated with this registry; however, is currently unknown but will be determined through custodian contact.
- Data access to registries is often complex, due to the application requirements, ethical approval processes and policies behind transfer of data; these complexities often cause long timelines receipt of aggregated data. ARW and Pfizer are currently in communication with data custodians to understand the feasibility of accessing the registry and ways of accessing registry data. If registry access is required, ARW will conduct the necessary processes to allow for efficient data access.
- The Austrian Myeloid Registry had reduced data collection in recent years due to the COVID-19 pandemic. Consequently, the current number of patients treated with GO with data available in the registry is relatively low. Nonetheless, data collection should increase in the coming months enabling more GO-treated patient data. The timeline for data collection should align with eCRF-based data collection for the Austrian, Belgian and German sites, as a result, data extraction and analysis should align with the both the registry and site-collected data.

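### Registry follow-up runs to the extraction date although the registry's lag is unknown; if there is a lag, registry OS, EFS and RFS are biased upward

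*Protocol*

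**What the plan says.** Protocol section 9.2 (Setting) first gives a general rule for all patients: "Follow-up will end with the following endpoints: death, loss of data (eg, transfer to a new hospital) or end of the study period". It then sets the end of follow-up for the survival outcomes by source. For the chart-review sites, "follow-up will extend up until either the last data available for the patient (in Austrian, Belgium, and German sites"); for the registry the end is different: "or the date of database extraction (in the Austrian Myeloid Registry"). Patients with too little follow-up "will be right-censored for the purpose of survival outcome specific analysis", but no censoring date is named.

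Section 9.9 (Limitations) says of the same registry: "The Austrian Myeloid Registry may not have data for patients available to the present day". Its lag "is currently unknown but will be determined through custodian contact". Nothing in the protocol ties that lag, once known, to the end of follow-up or to censoring.

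Sections 9.3 and 9.6 plan to harmonise the sources and combine them in one dataset. Section 9.7 plans Kaplan-Meier curves and allows analyses restricted to patients from certain data sources.

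**The concern.** Kaplan-Meier estimation needs each patient's time at risk to stop where observation of events stops. If a record is complete only to some date before extraction, a later death or relapse is invisible. Carrying that patient to extraction as event-free drops the event from the numerator and keeps the time in the risk set. The error goes one way: the curve is too high.

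Chart-review patients, whose follow-up ends at their last data, do not have this problem. The combined curve would therefore mix two definitions of follow-up, and any registry-only or by-source survival result would carry the full bias. This is a stated rule, not a detail left for the SAP, and it gives the wrong answer whenever the lag exceeds zero.

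**Working it through.** **Inputs from the protocol**
- Indexing period 1 April 2018 to 31 May 2023, i.e. 62 months (section 9.2).
- Expected patients by source (section 9.5, Table 1): 50 + 30 + 50 + 42 + 18 + 40 = 230, which reproduces the stated total. The registry share is 30/230 = 13.0%.
- Illustrative medians from the GO arm of the cited phase 3 trial (section 7): OS 27.5 months, EFS 17.3 months.
- End of data collection 30 April 2024 (Abstract; section 6). No extraction date is stated.

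**Assumptions**
- Exponential event times and uniform entry over the 62 months.
- Extraction at month 73 (30 April 2024). As an early variant, month 67 (1 November 2023, the Abstract's start of data collection; section 6 gives 1 November 2024, which is after its own end date).
- A lag L of 0, 3, 6, 12 or 18 months. The protocol gives no figure. Every event in the last L months before extraction is taken as unrecorded.
- Patients with under 3 months of visible data and no recorded event are left out.

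**True values.** S(24) = 2^(−24/median). OS: 2^(−24/27.5) = 0.546. EFS: 2^(−24/17.3) = 0.382.

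**Mechanism.** Let a patient's data be complete to time X after index (extraction minus L minus entry). Under extraction-date censoring, patients with X < t and no recorded event stay in the risk set at t but cannot contribute an event. The estimated hazard at t is the true hazard multiplied by the share of the risk set with X ≥ t. That share is at most 1, and below 1 once L > 0 and t is late enough.

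**Registry results, censoring at extraction (month 73; simulation of 200,000 patients)**

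| Lag (months) | 24-month OS | Median OS (months) | 24-month EFS | Median EFS (months) | Deaths unrecorded |
|---|---|---|---|---|---|
| 0 | 54.5% | 27.5 | 38.2% | 17.3 | 0% |
| 3 | 55.7% | 28.7 | 39.5% | 17.7 | 5% |
| 6 | 57.1% | 30.2 | 41.2% | 18.5 | 10% |
| 12 | 59.6% | 34.3 | 44.5% | 19.9 | 22% |
| 18 | 61.3% | 40.9 | 46.6% | 20.8 | 34% |

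Numerical integration of the hazard expression above gives the same 24-month values to within about 0.1 point.

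With extraction on 1 November 2023 the bias is slightly larger. At a 12-month lag, 24-month OS is 60.3% and the median is 35.6 months.

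**Same data, censoring at the last recorded data.** Over both extraction dates and all lags, 24-month OS is 54.4% to 54.5% with a median of 27.3 to 27.5 months. EFS is 38.0% to 38.4% with a median of 17.2 to 17.4 months. The bias disappears.

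**Pooled effect on 24-month OS.** Shift ≈ 0.130 × (registry shift):
- 3 months: 0.130 × 1.2 = 0.2 points
- 6 months: 0.130 × 2.6 = 0.3 points
- 12 months: 0.130 × 5.1 = 0.7 points
- 18 months: 0.130 × 6.8 = 0.9 points

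Simulating the pooled curve directly gives 55.3% at a 12-month lag and 55.5% at 18 months, against 54.6% with no lag. The pooled median moves from 27.5 to 28.2 and 28.5 months. At 36 months with an 18-month lag the pooled shift is 42.1% − 40.4% = 1.7 points.

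**The case against.** The strongest defence is that section 9.2 describes a data-capture window, not a censoring date. On that view a record that stops being updated counts as loss of data under the general rule, and the SAP may set the date for each patient. Part of this stands: no sentence says outright that a registry patient with an out-of-date record is treated as alive at extraction, so the bias has to be stated conditionally. But the example given for loss of data is a hospital transfer, the right-censoring sentence names no date, and the only registry-specific end point is extraction, set in direct contrast to last available data at the sites. If loss of data was meant to cover registry lag, the text still needs to say so.

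It can also be said that the lag is disclosed, is to be established with the custodian, and may be short. That is true, and at zero lag there is no bias. Knowing the lag helps only if the rule uses it.

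The practical effect on the pooled result is small. A simple binomial 95% interval at 55% with 230 patients is about ±1.96 × √(0.55 × 0.45/230) = ±6.4 points, well above the pooled shift. With 30 patients it is about ±17.8 points. Survival is a secondary, descriptive objective, and no registry-versus-site survival comparison is specified.

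Three stronger readings are tempting, and the protocol does not support them:
- **Reduced collection as proof of stale records.** Section 9.9 also says "The Austrian Myeloid Registry had reduced data collection in recent years due to the COVID-19 pandemic". The consequence it draws is a low number of GO-treated patients in the registry, not out-of-date records for those enrolled.
- **Upward bias in time to next treatment.** Section 9.3.2.2 specifies this only as a continuous number of days to the next line. If it is summarised among patients who had a next line, the extraction date does not enter.
- **Extraction is never a valid censoring date.** It is valid if the custodian confirms that records are complete to that date.

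**Conclusion.** The point holds in conditional form. The protocol sets a registry-specific end of follow-up that biases OS, EFS and RFS upward if the registry has a lag and event-free patients are censored at extraction. A reader might infer that registry survival is certainly inflated. The protocol does not show that, because it anticipates a lag but does not quantify one.

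Under the stated assumptions and lags of 3 to 18 months, registry 24-month OS would read about 56% to 61% against about 54.5%. The pooled 24-month shift is about 1 point or less. These sizes rest on exponential times, trial medians used only for illustration, an assumed extraction date, and a lag that hides every recent event for every registry patient. RFS was not simulated; its direction follows from the same mechanism. The weight of the point lies in registry-only or by-source results and in having one definition of follow-up, more than in the pooled curve.

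**What to change.** In section 9.2, replace the two source-specific ends of follow-up with one censoring rule for OS, EFS and RFS: a patient without the event is censored at the last documented contact or status date. Ask the registry for that date. If it cannot be supplied, censor at a data-complete date confirmed by the custodian, which may equal the extraction date only if completeness to extraction is confirmed. Add to the lag statement in section 9.9 that the confirmed lag will be used to set this date.

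The cost is one extra field in the registry request, one changed sentence in section 9.2 and slightly shorter registry follow-up. Section 9.6 already allows specific variables to be requested from the registry and aligned with the eCRF. Because registry data arrive anonymised, the field should be specified before extraction.

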9.2.1. Inclusion Criteria

Patients must meet all of the following inclusion criteria to be eligible for inclusion in the study:

1. Patient has a clinical diagnosis of **de novo** AML.
2. Patient is aged 18 years or older.
3. Patient has a cytogenetic risk stratification of 'favourable' or 'intermediate (classified according to the International System for Human Cytogenic Nomenclature criteria.¹³

4. Patient has been treated with GO in a 1L induction setting in a combination chemotherapy treatment.
5. Patient has data points available for a minimum of 3 months data from the first GO-containing regimen (index). Patients who die within the 3 months are eligible for inclusion within the study.
6. *For patients from Austrian, Belgium, and German sites:* Evidence of a personally signed and dated informed consent document indicating that the patient (or a legally acceptable representative) has been informed of all pertinent aspects of the study.
Note – may not be required and depends on individual country/site IRB guidance.

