Gemtuzumab ozogamicin (GO) [Mylotarg®] is an antibody-drug conjugate used for the treatment of AML patients with myeloid cells that express the CD33 receptor.¹⁰ The FDA approved GO for the treatment of newly diagnosed CD-33-positive AML in September 2017.¹ for use alone or in combination with chemotherapy, depending on the characteristics of the patient. In April 2018, GO received marketing authorisation from the EMA for the European Union, to be used in combination with daunorubicin and cytarabine chemotherapy.^{11,12} The ALFA-0701 multicentre Phase 3 trial results demonstrated the effectiveness of GO, which ultimately led to its approval. Patients aged 50-70 years old with newly-diagnosed de novo AML were treated with GO in combination with daunorubicin and cytarabine chemotherapy. The trial demonstrated an estimated median event-free survival (EFS) of 17.3 and 9.5 months for patients receiving GO and chemotherapy or chemotherapy alone respectively and 27.5 and 21.8 months for overall survival (OS).¹

Over the years GO has been studied in multiple different combination regimens and different dosing schemes.¹² There is limited knowledge of its real-world use and outcomes as first line treatment with the recent licensed dosing (ie, 3 doses during the induction cycle). Using results from a feasibility study conducted by Adelphi Real World (ARW) and contacts with data source custodians, evidence suggests that 1L treatment with GO has been used to treat AML patients in several countries. Pfizer would like to conduct a study investigating the treatment patterns and effectiveness outcomes of 1L GO use on de novo AML patients in real-world healthcare, specifically those in the favourable and intermediate risk groups. This will allow the assessment of whether GO prescription patterns are aligned with licensed dosing/guidelines and will provide novel insights into whether the observed real-world outcomes associated with these prescription patterns are effective. The study will use a combination of AML specific data sources and a retrospective medical chart review using a Case Report Form (CRF) to conduct a multi-country study with Belgium and Austria. Such data sources were identified during a feasibility assessment and were deemed to likely capture a sufficient sample size of patients (according to the eligibility criteria outlined in [Section 9.2](#)).

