8. RESEARCH QUESTION AND OBJECTIVES

This study aims to answer the following research question:

How is GO being used in real world clinical practice of de novo intermediate/favourable risk AML patients and what are the outcomes?

Co-Primary objectives

- To describe the patient demographics and clinical characteristics of patients treated with GO in intermediate and favourable cytogenetic risk, de novo AML.
- To describe GO treatment patterns in the study population, including:
 - Combination chemotherapy regimen
 - GO use in induction and consolidation
 - Number of doses of GO
 - Timing of GO doses in 1L treatment
 - GO dosage

Secondary objective

- To describe 1L treatment effectiveness outcomes for the study population, including:
 - Time-to-next treatment
 - Survival (EFS, RFS, OS)

Exploratory objective

- To describe MRD (minimal residual disease) status for the study population.

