9.2.2. Exclusion Criteria

Patients meeting any of the following criteria will not be included in the study:

1. Patient has been exposed to any other ‘non-GO’ treatment regimen prior to treatment with GO for their AML (except leukoreduction with and without hydroxyurea).
2. Patient has been treated with GO only as a consolidation therapy and not as induction.

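### The protocol neither excludes nor identifies patients whose first-line GO was given inside an interventional trial, so any such patients would count as real-world prescribing

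*Protocol*

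**What the plan says.** Section 8 of the protocol frames the research question as "How is GO being used in real world clinical practice of de novo intermediate/favourable risk AML patients and what are the outcomes". Section 7 states what the treatment-pattern results are for: "This will allow the assessment of whether GO prescription patterns are aligned with licensed dosing/guidelines".

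Eligibility is broad by intention. Section 9.2 says "There are minimal inclusion/exclusion criteria", with the purpose given as "in order to maximize the number of GO-treated patients eligible for this study", and sites must enter every eligible patient. The inclusion criterion on exposure (Section 9.2.1, criterion 4) is "Patient has been treated with GO in a 1L induction setting in a combination chemotherapy treatment". The two exclusion criteria in Section 9.2.2 concern exposure to a non-GO regimen before GO, and the case "Patient has been treated with GO only as a consolidation therapy and not as induction".

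None of the six inclusion and two exclusion criteria mentions an interventional trial. Nor do the exposure definition (9.3.1), the treatment-pattern and effectiveness variables (9.3.2), the baseline covariates (9.3.3) or the limitations (9.9).

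**The concern.** For a patient treated inside a trial, the number, dose and timing of GO and the partner chemotherapy are set by the trial protocol. Those are the co-primary items listed in Section 8. Such a patient says nothing about how physicians prescribe GO, or whether their prescribing agrees with the licence, yet satisfies every criterion as written.

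Two features of the plan make the gap harder to repair later. First, Section 9.9 expects that, where only a total GO dose is recorded, the number of doses could be imputed from prescribing guidelines; that reasoning does not carry over to a patient dosed under a trial protocol. Second, Sections 9.6, 9.8 and 9.9 say that German data are fully anonymised with no linkage file, so an item not collected at entry cannot be recovered there. Germany contributes 40 of the expected 230 patients (17%).

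EFS and OS could also be affected, since trial participants are selected and managed by protocol. The document gives no basis for a direction or size, so the arithmetic below is confined to the dosing results.

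**Working it through.** **Plan's own figure.** The Table 1 rows sum to 50 + 30 + 50 + 42 + 18 + 40 = 230, which reproduces the stated total of about 230.

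**Is there a rule elsewhere that closes the gap?**
- Section 9.1 says that assessments are part of normal practice. That describes this study's own assessments. It does not restrict how GO came to be given.
- Section 9.3.1 requires GO and another chemotherapy drug within the first-line regimen. It does not ask whether this was routine care.
- Section 9.9 allows subgroups by similar regimen or dosing schedule. A subgroup with an atypical schedule mixes patients prescribed that schedule with patients allocated it in a trial. A trial schedule that matches the licence would not stand out at all.

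None of these excludes or identifies a trial patient.

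**Size, under stated assumptions.** The protocol gives neither the share of trial patients nor the expected conformity with licensed dosing. Assume:
- p = share of trial patients: 0, 5, 10 or 15%
- routine share receiving the licensed number of doses: 85%
- q = share of trial patients receiving that number: 0, 50 or 100%

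Pooled share = 0.85(1 − p) + qp, so shift = p(q − 0.85).

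| p | patients of 230 | q = 0: pooled (shift) | q = 0.5: shift | q = 1: pooled (shift) |
|---|---|---|---|---|
| 0% | 0 | 85.0% (0) | 0 | 85.0% (0) |
| 5% | 11.5 | 80.75% (−4.25) | −1.75 | 85.75% (+0.75) |
| 10% | 23 | 76.5% (−8.5) | −3.5 | 86.5% (+1.5) |
| 15% | 34.5 | 72.25% (−12.75) | −5.25 | 87.25% (+2.25) |

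**Sampling error for comparison.** The 95% half-width at 85% and n = 230 is 1.96 × √(0.85 × 0.15 / 230) = 4.6 points. With q = 0, the shift reaches this at p = 4.6/85 = 5.4%. With q = 1, it stays below it throughout the assumed range. A larger sample would shrink the half-width but not the shift.

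**Precision lost by setting flagged patients aside.** At a proportion of 50%, where the interval is widest, the half-width is 1.96 × √(0.25/230) = 6.46 points. If 10% are removed it is 1.96 × √(0.25/207) = 6.81 points, a loss of about 0.35 points.

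**The case against.** The strongest reply is that the premise is not shown. Nothing in the protocol says that any patient at these sites or in the registry received GO in a trial during the indexing period, which begins in April 2018 to follow EMA approval. The background remark in Section 7, "Over the years GO has been studied in multiple different combination regimens and different dosing schemes", might be read as evidence of trial dosing in this cohort. It is not: it describes the history of GO, and the text goes on to contrast it with recent licensed dosing. That several sources are university or high-volume hospitals is likewise no evidence; Sections 9.2 and 9.4 say sites are selected on feasibility, including GO caseload and data availability. This part of the reply stands.

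The magnitude is also open to challenge. The 13-point figure needs both the highest assumed share and not one trial patient on the licensed number of doses. Most cells in the table lie within sampling error. This stands too: the figures are bounds under assumptions, not forecasts.

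The eCRF screener is not shown, Section 9.4 says abstracted data are not limited to the listed items, and Section 9.3 leaves final variables to the SAP. A flag may therefore exist elsewhere. Eligibility, however, is fixed in the protocol, and a SAP cannot create an item that was not collected.

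Finally, broad eligibility is a deliberate choice to maximise a small cohort. That weakens the case for outright exclusion. It does not weaken the case for knowing which patients were treated in a trial.

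**Conclusion.** The gap is confirmed from the text. The criteria and the variable list admit patients given GO under an interventional trial protocol and offer no way to identify them, although the co-primary results are meant to describe routine prescribing and its agreement with the licence.

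Whether it affects the results is unknown. A reader might infer that trial-dictated dosing is in fact present in the co-primary results, or that an error of 13 points is to be expected. The document supports neither. The shift is zero if there are no trial patients. Under assumed shares of 5-15% and 85% routine conformity it is about 1-2 points if all trial patients match and 4-13 points if none do, against a half-width of about 5 points. The direction depends on whether trial schedules were closer to or further from licensed dosing. Without the item, the sponsor could not show that the shift was zero. The point is worth correcting because the remedy is small and, for the German records, cannot be applied after entry.

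**What to change.** Before data entry, add one item to the eCRF screener and to the Austrian Myeloid Registry data request: was first-line GO received within an interventional clinical trial (yes / no / unknown)? Base the main treatment-pattern and effectiveness tables on patients not flagged yes, and show the same tables with flagged patients included as a sensitivity analysis. Report the number of unknowns by data source, since they remain in the main tables.

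This keeps all eligible patients in the study, consistent with the aim in Section 9.2. Excluding trial patients outright is an alternative, but is harder to square with that aim.

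Costs:
- A small protocol and eCRF amendment, needing prospective IRB/IEC approval under Section 10.4. Time is short: the protocol is dated 19 October 2023 and its abstract plans data collection from 01 November 2023 (Section 6 gives 01 November 2024, which needs reconciling).
- Possible unknown values from the registry, whose variables Section 9.3 says are not fully known, and from any German record entered before the item is added.
- A slightly smaller main analysis set: about 0.35 points of precision if 10% are set aside.

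### The 3-month data requirement, waived only for deaths, removes patients whose data stop while they are alive; this lowers the OS curve slightly and discards usable co-primary data

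*Protocol*

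**What the plan says.** Criterion 5 in Protocol 9.2.1 reads "Patient has data points available for a minimum of 3 months data from the first GO-containing regimen (index" date), and continues: "Patients who die within the 3 months are eligible for inclusion within the study". Section 9.2 gives the reason for the waiver: "Patients who die within the 3-month follow-up period would be considered eligible for inclusion in order to evaluate EFS, RFS and OS outcomes". It gives the reason for the minimum as well: "Patients must have data available for a minimum of 3 months after initiation of GO-regimen to capture data relating to effectiveness outcomes". It adds that 3 months lets treatment patterns and early effectiveness be assessed.

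The same section states: "Follow-up will end with the following endpoints: death, loss of data (eg, transfer to a new hospital) or end of the study period". Patients whose follow-up is too short for the survival outcomes "will be right-censored for the purpose of survival outcome specific analysis". Section 9.7 plans Kaplan-Meier curves. Section 9.2 also describes the criteria as minimal, "in order to maximize the number of GO-treated patients eligible for this study".

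**The concern.** Of the three ways follow-up can end, the criterion exempts death. That leaves "loss of data (eg, transfer to a new hospital) or end of the study period", and at the chart sites the calendar cannot bring the second into play before 3 months. The rule therefore selects on a post-index outcome: every early death stays, while a patient with the same early history whose record stops alive is taken out.

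Two things are at stake. First, the early OS risk sets lose living patients but keep all the deaths. Second, the rule governs the whole study population, so these patients also drop out of the co-primary description of characteristics and GO dosing. Section 7 places the licensed GO doses within the induction cycle, so a patient transferred after induction may have a full induction record.

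The SAP cannot repair this. Section 9.4 has sites run an eligibility screener before any data are abstracted, so a chart patient who is screened out never reaches the database. The limitations in 9.9 mention the 3-month minimum only as a limit on how far OS and EFS can be assessed, not as a selection.

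**Working it through.** **Plan's own figure.** The source estimates in Table 1 (9.5) sum to 50 + 30 + 50 + 42 + 18 + 40 = 230, as stated.

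**Calendar.** Indexing closes on 31 May 2023 (9.2). The Abstract starts data collection on 1 November 2023; the Milestones table (Section 6) says 1 November 2024. On the earlier date the gap is 154 days, or 154/30.44 = 5.06 months. Administrative cut-off therefore cannot leave a chart patient with less than 3 months. For the registry, 9.9 says the data may not run to the present day and that the lag is unknown, so the same conclusion cannot be drawn there.

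**Direction for OS.** At each death time before 3 months, Kaplan-Meier multiplies by 1 − d/n. The rule leaves d unchanged and can only reduce n, so each factor is equal or smaller. After 3 months the risk sets are the same with or without the rule, so the ratio reached at 3 months carries through the rest of the curve.

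**Size.** The assumptions are independent exponential death and loss over 3 months, with probabilities q and L. Then:

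- alive and followed: A = (1 − q)(1 − L)
- observed death: D = [ln(1 − q) / (ln(1 − q) + ln(1 − L))] × (1 − A)
- 3-month OS under the rule: A / (A + D), against a true value of 1 − q
- fraction removed: 1 − A − D

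| q / L (assumed) | A | D | OS under rule | True OS | Difference (points) | Removed of 230 |
|---|---|---|---|---|---|---|
| 5% / 5% | 0.9025 | 0.0488 | 94.9% | 95.0% | 0.1 | 11 |
| 10% / 10% | 0.8100 | 0.0950 | 89.5% | 90.0% | 0.5 | 22 |
| 15% / 20% | 0.6800 | 0.1348 | 83.45% | 85.0% | 1.55 | 43 |

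For the middle row, 0.81 / (0.81 + 0.095) = 0.81/0.905 = 0.895, and 230 × 0.095 = 21.9.

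**Anchored to the protocol's own survival figure.** Section 7 cites a median OS of 27.5 months in the GO arm of the phase 3 trial. If survival is exponential, 3-month mortality is 1 − 0.5^(3/27.5) = 7.3%. The understatement is then 0.07, 0.18, 0.37 and 0.82 points at assumed losses of 2%, 5%, 10% and 20%, with about 4, 11, 22 and 44 of 230 removed.

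**Check by simulation** (100,000 patients, 27.5-month median, 10% loss). With lost patients kept and censored, 3-month OS is 0.927 against a true 0.927. Under the protocol's rule it is 0.924. At 24 months the rule gives 0.544 against 0.546.

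**Denominator.** The Abstract calls the 230 expected to be eligible, whereas Table 1 labels its counts as patients treated with GO. The counts above take 230 as the number before criterion 5. If 230 is already the number after it, the middle case starts from 230/0.905 = 254 patients and 24 are removed.

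**The case against.** The strongest objection is size. With n = 230, the binomial 95% half-width, 1.96 × √(S(1 − S)/230), is about 2.8, 3.9 and 4.6 points at S = 0.95, 0.90 and 0.85. The three understatements are well inside these, the largest needs an assumed 20% loss within 3 months, and the study tests no hypothesis. This stands: the OS bias is modest.

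Second, a reader might infer that early mortality is certainly overstated. The documents do not support that. The rule's curve cannot lie above the censored curve, but if patients who leave have a worse prognosis, the censored curve is itself too high and the rule's curve could be nearer the truth.

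Third, a reader might extend the downward bias to EFS. Its events in 9.3.2.2 include relapse and failure to reach remission, so a patient who fails induction and then transfers is removed together with that event. The direction can be mixed, and relapse-free survival (RFS) raises the same difficulty.

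Fourth, a reader might conclude that only transferred or lost patients are affected and that the indexing window already guarantees 3 months. Registry lag prevents both conclusions for that source, which Table 1 puts at about 30 patients.

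Fifth, the treatment-pattern rationale has some force. Section 8 covers GO in both induction and consolidation, and a patient lost after induction has unobserved consolidation; one lost during induction has incomplete induction dosing too. This is a reason to choose denominators carefully, not to exclude the patient.

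Finally, the waiver for deaths is deliberate and avoids the larger error of dropping early deaths. The fault is in the 3-month requirement, not in the waiver.

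**Conclusion.** The point holds in limited form. Criterion 5 conditions entry on follow-up after index and removes patients whose data stop while they are alive. The survival analysis does not need it, because short follow-up is already right-censored, and at chart sites the calendar does not call for it.

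That the OS curve is equal or lower than with these patients kept and censored follows without any assumption about hazards. That 3-month OS is understated relative to the truth requires non-informative loss, and the sizes also require the assumed rates and constant hazards: from about 0.1 to 1.55 points across the three scenarios, and under 1 point at the protocol's cited median even with 20% loss. No direction is claimed for EFS.

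The avoidable loss of baseline and observed induction-dosing data probably matters more than the OS bias. It runs against the stated aim of maximising eligible patients, and for chart patients it cannot be undone at analysis. A change before abstraction is worthwhile.

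**What to change.** Remove the 3-month data requirement from criterion 5 and from the matching text in the Abstract and 9.2. Include every patient who meets criteria 1–4 and the consent rule, meets no exclusion criterion, and has an index date in the window. Then:

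- describe baseline characteristics and induction GO dosing in all of them, with unobserved doses shown as missing;
- report consolidation GO, and GO in both phases, among patients observed through that phase, or as unknown; do not count unobserved consolidation as no GO;
- censor OS, EFS and RFS at the last documented contact;
- keep the 3-month restriction only as a sensitivity analysis.

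The cost is protocol wording, an edit to the eCRF screener, and abstraction of some patients with short follow-up and incomplete consolidation data.
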